20.1.6 Change in FBG levels at Weeks 4, 8, and 12 from baseline

Variables:

- The question "Blood glucose concentration (mg/dL) before breakfast" in eCRF "Blood Glucose Monitoring (7-point reading)" form
- Start date of concomitant medication (From eCRF form: "Concomitant Therapy: Special Interest Hyperglycaemia (For rescue medication)")
- Date of first dose administration
- Date of collection of FBG at week 12.

Derivations:

- Change in FBG level = Post visit Baseline visit
- If start date of concomitant medication (Special form) > Date of first dose administration, then this FBG result data will not be considered for analysis and we will consider this value as missing.
- If week 12 (FBG results) = missing or start date of concomitant medication (Special form) < Date of collection of FBG at week 12, then we will use LOCF i.e. previous visit value we will carry forward to visit (week 12).

20.1.7 Self-monitored 7-point SMBG levels at baseline, Weeks 4, 8, 12, and 24

Variables:

Below each Self-monitored 7-point SMBG level will be captured in eCRF "Blood Glucose Monitoring (7-point reading)" form

- Blood glucose concentration (mg/dL) before breakfast
- Blood glucose concentration (mg/dL) 2 hours after morning meal
- Blood glucose concentration (mg/dL) before midday meal
- Blood glucose concentration (mg/dL) 2 hours after midday meal
- Blood glucose concentration (mg/dL) before evening meal
- Blood glucose concentration (mg/dL) 2 hours after evening meal

Blood glucose concentration (mg/dL) at 3AM (± 1 hour)

Derivations: Not Applicable

20.1.8 Change in 7-point SMBG levels at Weeks 4, 8, 12, and 24 from baseline

Variables:

- All in above secondary endpoint (section 20.1.7) mentioned variables are applicable for this endpoint.
- Start date of concomitant medication (From eCRF form: "Concomitant Therapy: Special Interest Hyperglycaemia (For rescue medication)")
- Date of first dose administration
- Date of collection of 7-point SMBG levels at week 24.

Derivations:

- Change in 7-point SMBG levels = Post visit Baseline visit
- If start date of concomitant medication (Special form) > Date of first dose administration, then this 7-point SMBG levels will not be considered for analysis and we will consider this value as missing.
- If week 24 (7-point SMBG results) = missing or start date of concomitant medication (Special form) < Date of collection of 7-point SMBG levels at week 24, then we will use LOCF i.e. previous visit value we will carry forward to visit (week 24).

20.1.9 Intrasubject variability, as measured by the standard deviation (SD) of 7-point SMBG levels

Variables:

• All in above secondary endpoint (section 20.1.7) mentioned variables are applicable for this endpoint.

Derivations:

Intrasubject variability, $=\frac{S.D}{Mean} * 100(\%)$

Page 61 of 85

20.1.10 Basal insulin dose (U/day and U/kg/day)

Variables:

Amount of Dose (Units) (In eCRF "Exposure Form")

Derivations:

• Basal insulin dose $(U/kg/day) = \frac{Basal insulin dose (U/day)}{Weight (kgs)}$

Note: Weight at corresponding visit will be used.

20.1.11 Change in weight and body mass index at Week 24 from baseline

Variables:

- Weight (In eCRF "DEMOGRAPHICS" form)
- Body Mass Index (BMI) (In eCRF "DEMOGRAPHICS" form)

Derivations:

- Change in weight = Post visit Baseline visit
- Change in body mass index = Post visit Baseline visit

20.1.12 Change in Insulin Treatment Satisfaction Questionnaire (ITSQ) score at Week 24 from Week 4

Variables:

• ITSQ score (for each subject we have 22 questions each question with 7 point scale in eCRF "Insulin Treatment Satisfaction Questionnaire (ITSQ)" form)

Derivations:

Transformed domain
$$= 100 * \frac{7 - \text{Raw Doamin score}}{6}$$

Where, Raw domain score= mean of the items score in the domain for that subject

Transformed Overall = $100 * \frac{7 - \text{Raw Overall score}}{6}$

CONFIDENTIAL CS.BS.01.00 TPL-1.0: Statistical Analysis Plan Template

Page 62 of 85

Where, Raw overall score =mean of the items score for that subject

20.2 Analyses

- 20.2.1 Serious adverse events (SAEs) and treatment-emergent adverse events (TEAEs)
 - Population: FAS and PPS Stratification: Table: NA Listing: NA Statistics: The SAE and TEAE will be identified by using derivation mentioned in section 20.1.1. Summary statistics for SAEs and TEAEs will be presented as frequency and percentage (n and %) for table.

20.2.2 Rates per 30 days and per subject year of total hypoglycemic events (symptomatic or asymptomatic)

| Population: | FAS and PPS |
|-------------|-------------|
|-------------|-------------|

Stratification: Table: NA

Listing: NA

Statistics: The rate that is the number of hypoglycemic events per subject over the study period i.e. Day 0 to week 24/week 28 will be summarised as continuous variables as (n, mean, standard deviation, standard error, median, minimum, maximum).

> By using the formula mentioned in section 20.1.2, we will get the Rates per 30 days and per subject year (365.25 days) between two time points (i.e. baseline to end of treatment/study) and This Rates per 30 days and per subject year (365.25 days) will be summarised as (n, mean, standard deviation, standard error, median, minimum, maximum).

> Summary statistics and efficacy table will be presented separately for baseline to end of treatment and baseline to end of the study.

Page 63 of 85

The Negative Binomial Model without categorical variable i.e. the generalized linear model will be used with HbA1c as covariate and the log of the study treatment exposure time as offset variable.

The estimate, 95% confidence interval and p-value will be provided for efficacy table.

The Negative binomial regression equation is as follows:

Y = Offset variable + α + β (X)

Where,

Y= The response rate of 30 days and per subject year for total hypoglycaemic events.

Offset variable = The log of study treatment exposure time for rates per 30 days and per subject year (See section 20.1.2 for formula)

 $\alpha = Intercept$

 β =slope

X= Covariate i.e. Baseline HbA1c results

The hypothesis is as follows

H0: $\beta = 0$

i.e. The Rate of per 30 days and per subject year of total hypoglycaemic events not significantly differs depending on the Baseline HbA1c..

V/s

H1: β ≠ 0

i.e. The Rate of per 30 days and per subject year of total hypoglycaemic events significantly differs depending on the Baseline HbA1c. events.

The above hypothesis will be tested based on α (alpha)=0.05, if the p-value \geq 0.05 then we will conclude that there is no statistically significant change in rates per 30 days and per subject year of total hypoglycaemic events. i.e. Ho is accepted. The sample SAS programme is as follows for negative binomial model:

proc genmod data=Dataset;

model Response Rate=Baseline_HbA1c / cl dist=NB link=log offset= offset variable;

estimate "Model with Mean baseline HbA1C for rate per 30 days and per year" int 1 Baseline HbA1c observed mean / exp;

ods output estimates=Output dataset;

run;

quit;

20.2.3 Incidence and rates per 30 days and per subject-year of nocturnal, severe, documented symptomatic and asymptomatic hypoglycemic events

Population: FAS and PPS

Stratification: Table: NA

Listing: NA

Statistics: By using the formula mentioned in section 20.1.2, we will get the Rates per 30 days and per subject year (365.25 days) between two time points (i.e. baseline to end of treatment/study) for each hypoglycaemic events category separately.

> The incidence and rates per 30 days and per subject-year for each below mentioned hypoglycemic events will be analysed similarly as mentioned in section 19.2.1 for incidence and section 20.2.2 for rates of hypoglycemic events.

- Nocturnal hypoglycemia
- Severe hypoglycemia
- Documented symptomatic hypoglycemia, and
- Asymptomatic hypoglycemia

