### **10.3.2. Safety Analyses**

#### **10.3.2.1. Hypoglycemic Events**

The primary endpoint of this study is the incidence of total (symptomatic or asymptomatic with FBG level  $\leq 54$  mg/dL [3.0 mmol/L]) hypoglycemic events at Week 24. The events will be analyzed as following as number and percentage of subjects experiencing at least 1 event over the study period. A 95% confidence interval for the rate will be calculated using the normality assumption.

The rate of total (symptomatic or asymptomatic with FBG level  $\leq 54$  mg/dL [3.0 mmol/L]) hypoglycemic events will be analyzed as follows:

- Number of hypoglycemic events per subject over the study period will be analyzed as continuous variables as per Section 10.3.1 (mean, median, SD, standard error [SE], minimum, and maximum)
- The rate of hypoglycemic events per 30 days, and the rate per year, that is the number of hypoglycemic events per subject year (365.25 days), will be calculated.
  - The rate per 30 days between 2 time points (end of treatment/study vs. baseline) is defined as the total number of events between the time points divided by the actual number of days between the time points, and then multiplied by 30. A similar approach is then used for the number of events per subject-year (365.25 days).
  - These measures will be summarized for the overall study period and will be assessed using a negative binomial model with baseline HbA1c as covariate and the log of the study treatment exposure time as offset variable.

The following types of hypoglycemia (see Section 9.1.1) will be analyzed similarly (incidence and rates) as specified for total hypoglycemia:

- nocturnal hypoglycemia
- severe hypoglycemia
- documented symptomatic hypoglycemia, and
- asymptomatic hypoglycemia

All analyses for the hypoglycemic events will be repeated for the PPS population.

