6.2 Full Analysis Set (FAS) / Safety Analysis Set (SAF)

FAS and SAF are identical to each other as this is single arm trial and no randomization occurs. So, we will indicate this population as FAS for analysis purpose.

This population will include all enrolled participants who take at least 1 dose of study treatment.

 "Y" for subjects who received at least one dose of the investigational product (IMP). Else set to "N".

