20.1 Variables and derivations

20.1.1 Serious adverse events (SAEs) and treatment-emergent adverse events (TEAEs)

Variables:

- First Study drug administration Date
- Serious AE start Date
- Inform consent date
- Adverse Event Serious i.e. (AESER)

Derivations:

- If Adverse Event Serious i.e. (AESER) = "YES" and Serious AE start Date >= Inform consent date, then we will consider it as serious adverse event (SAE)
- If AE start Date >= First Study drug administration date, then we will consider it as treatment-emergent adverse events (TEAEs)

20.1.2 Rates per 30 days and per subject year of total hypoglycemic events (symptomatic or asymptomatic)

Variables:

- What was the blood glucose level (mg/dL) prior to treating the event? (In eCRF "Hypoglycemia Events" form)
- Were signs/symptoms of hypoglycemia present, other than the blood glucose reading? (In eCRF "Hypoglycemia Events" form)
- Hypoglycemic event start date
- Date of Visit 2 (Week 0)
- Date of Visit 8 (Week 24)
- Date of Visit 9 (Week 28)
- Date of first IMP dose administration (In eCRF "Exposure" form)
- Date of last IMP administration (In eCRF "End of Study" form)

Derivations:

- The symptomatic and asymptomatic i.e. total hypoglycemic events will be identified based on derivation mentioned in section 19.1.1.
- Hypoglycemic event start date ≥ Date of Visit 2 (Week 0) and Hypoglycemic event start date ≤ Date of Visit 8 (Week 24) for accessing the hypoglycemic events from Day 0 to week 24.
- Hypoglycemic event start date ≥ Date of Visit 2 (Week 0) and Hypoglycemic event start date ≤ Date of Visit 9 (Week 28) for accessing the hypoglycemic events from Day 0 to week 28.

The formula used for calculation for rates per 30 days and per subject year (365.25 days) of total hypoglycemic events mentioned below:

The rate of hypoglycemic events per 30 days $= \frac{\text{"The total number of events between the time points"}}{\text{"Actual number of days between the time points"}} * 30$ The rate of hypoglycemic events per year (365.25 days) $= \frac{\text{"The total number of events between the time points"}}{\text{"Actual number of days between the time points"}} * 365.25$ Offset variable for per 30 $= log \left(\frac{\text{"The Duration of treatment exposure"}}{30}\right)$ Offset variable per year $= log \left(\frac{\text{"The Duration of treatment exposure"}}{365.25}\right)$

Note: For the duration of treatment exposure see formula mentioned in section 12.1

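### Descriptive hypoglycaemia rates are unweighted means of each subject's own rate, so in the FAS one very early leaver can dominate them when events are few

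*SAP*

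**What the plan says.** Protocol 10.3.2.1 defines the rate per 30 days as the number of events between two time points "divided by the actual number of days between the time points, and then multiplied by 30", with the same approach for 365.25 days. It does not say whether the ratio is formed per subject or over all subjects together.

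SAP 20.1.2 uses the same ratio, with the denominator "Actual number of days between the time points". SAP 20.2.2 starts from a subject-level quantity, "The rate that is the number of hypoglycemic events per subject over the study period", and then turns to the two rates: "This Rates per 30 days and per subject year (365.25 days) will be summarised". Both the count and the rates "will be summarised as (n, mean, standard deviation, standard error, median, minimum, maximum"), in separate tables to end of treatment and to end of study. No exposure weight, minimum exposure or pooled rate is specified.

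SAP 20.2.3 repeats the step for each subtype ("we will get the Rates per 30 days and per subject year (365.25 days) between two time points") and has the subtypes "analysed similarly as mentioned in section 19.2.1 for incidence and section 20.2.2 for rates of hypoglycemic events".

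The FAS has no minimum follow-up. SAP 6.2 states: "This population will include all enrolled participants who take at least 1 dose of study treatment". Protocol 5.2 plans for 250 enrolled and 20% drop-out, and Protocol 8.2 lists persistent hypoglycaemia among the grounds for leaving the study.

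A negative binomial model with baseline HbA1c as covariate and log exposure as offset is planned alongside (Protocol 10.3.2.1, SAP 20.2.2). SAP 20.2.2 defines the response Y as the rate, and its sample code also names the response as a rate.

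**The concern.** A mean with SD, SE, median, minimum and maximum needs one value per subject. The reported figure is therefore the average of individual rates, and a subject seen for 7 days has the same weight as one seen for 168. One event in a short follow-up becomes a very large annual rate and enters the mean at full weight.

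Rates per 30 days and per subject-year are named secondary safety endpoints for total hypoglycaemia and for four subtypes. A reader will take the tabulated figure as events per subject-year of treatment. For a rare subtype such as severe hypoglycaemia, it could instead reflect the exit day of one person. Because hypoglycaemia is itself a ground for leaving, short follow-up and events may also go together.

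**Working it through.** **The plan's own figures.** The documents state no event rate per subject-year, so there is none to reproduce. The incidences in Protocol 5.2 do reproduce: 5/46 = 10.9% (11%) and 146/489 = 29.9% (30%). They are used below.

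**Inputs from the documents.** N = 250 (all taken to be in the FAS); 24 weeks = 168 days of treatment; incidence 11% or 30%.

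**Assumptions not in the documents.** Events per affected subject (1 or 5); one leaver with one event; the exit day; all others complete 168 days.

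**Formulas**, with y events and t days for each subject:
- Unweighted mean, as planned: (1/N) × Σ(365.25 × y/t).
- Pooled rate: 365.25 × Σy / Σt.

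**Contribution of one event to the unweighted mean of 250**

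| Exit day | Individual rate per year | Added to the mean |
|---|---|---|
| 3 | 365.25/3 = 121.75 | 0.487 |
| 7 | 365.25/7 = 52.18 | 0.209 |
| 14 | 365.25/14 = 26.09 | 0.104 |
| 28 | 365.25/28 = 13.04 | 0.052 |
| 168 (completer) | 365.25/168 = 2.174 | 0.0087 |

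**Whole-trial figures with one exit at day 7.** Total time is 249 × 168 + 7 = 41,839 days.
- 11% incidence, 28 subjects with one event each. Unweighted: (27 × 2.174 + 52.18)/250 = 0.444. Pooled: 28 × 365.25/41,839 = 0.244. Ratio 1.81; the leaver supplies 0.209/0.444 = 47% of the mean.
- 30% incidence, 75 subjects with one event each. Unweighted: (74 × 2.174 + 52.18)/250 = 0.852. Pooled: 75 × 365.25/41,839 = 0.655. Ratio 1.30.
- Subtype with 3 events in total. Unweighted: (2 × 2.174 + 52.18)/250 = 0.226. Pooled: 3 × 365.25/41,839 = 0.0262. Ratio 8.6; the leaver supplies 92% of the mean.
- 30% incidence, 5 events in each of the other 74 affected subjects. Unweighted 3.426, pooled 3.239. Ratio 1.06.

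**Bias and precision.** Trials were simulated with 50 of 250 subjects leaving at uniformly distributed times from day 1, independently of events, and with a constant event rate per subject. There were 4,000 trials per scenario. Both estimators averaged the true rate. SDs of the estimates (rate per year):

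| Incidence, dispersion | Unweighted | Pooled | Variance ratio |
|---|---|---|---|
| 11%, 1 | 0.068 | 0.054 | 1.59 |
| 11%, 5 | 0.091 | 0.076 | 1.43 |
| 30%, 1 | 0.148 | 0.113 | 1.72 |
| 30%, 5 | 0.352 | 0.345 | 1.04 |

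The unweighted mean exceeded 1.5 times the pooled rate in 0.1% to 1.4% of trials. Drop-out from day 14 or day 28 instead of day 1 brings the variance ratio much closer to 1.

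**The negative binomial model as written.** On the yearly scale the response is y × 365.25/t and the offset is log(t/365.25). Exposure is then divided out twice. For a completer the fitted rate is multiplied by 365.25/168 = 2.17.

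**The case against.** The strongest reply is that the plan already has an exposure-adjusted analysis. A count model with a log-exposure offset does not give a 7-day subject the weight of a completer, and the Protocol synopsis lists the number of events per subject among the quantities modelled. A reader might go the other way and infer that the plan ignores exposure; it does not. The reply fails only because the SAP writes the response as the rate. With counts as the response, an adjusted rate with a 95% CI would exist, and this point would reduce to a descriptive row.

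A reader might also infer that the totals are lost. They are not. Total events follow from n times the mean count, all hypoglycaemic events are listed (SAP 19.2.1), and each subject's exposure duration is listed (SAP 12.1 and 12.2). What is missing is a tabulated total of subject-time and the ratio itself.

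Other parts of the reply stand:
- No drop-out timing is documented, so exits at day 3 or 7 are hypothetical.
- Protocol 5.1.1 gives all subjects a follow-up visit 4 weeks after the last dose. If the end-of-study interval runs at least 28 days for leavers, one event adds at most about 0.05. The SAP bounds its windows by the Visit 8 and Visit 9 dates and does not state the end date for a subject without Visit 8.
- The analyses are repeated in the PPS, which excludes discontinuation before 24 weeks.
- The SD and maximum would expose an extreme subject. The median would not correct the mean, since it is 0 at 11% to 30% incidence.
- The primary endpoint is an incidence and is unaffected, and a single-arm study makes no comparison that turns on this mean.

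**Conclusion.** The point holds in a limited form. The descriptive rates are unweighted means of subject-level rates, and in the FAS a very early leaver with one event can dominate them when events are few. The risk is greatest for rare subtypes, moderate for total events at 11% incidence, and small when subjects have several events each (6% in the last case above). These sizes rest on the assumed exit day and events per subject.

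A reader might infer that the reported rate is biased, or that it will usually be dominated by one person. The documents do not support either. If drop-out is independent of events and the event rate is constant, the mean is unbiased and only less precise, and large discrepancies are uncommon. No single figure for the loss of precision belongs to the plan, because it depends on the event rate, the dispersion and the earliest drop-out day. Those two conditions may fail: Protocol 8.2 allows exit because of hypoglycaemia, and daily fasting glucose is mandatory only to Week 12, so asymptomatic events are easier to detect early. A distortion is then possible, but its size cannot be set from the documents.

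This is a cheap improvement to a named secondary endpoint, not a flaw in the primary analysis.

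**What to change.** In the SAP 20.2.2 and 20.2.3 tables:
- Add total events, total subject-years, and total events divided by total subject-time (× 30 and × 365.25). Label that ratio as the descriptive rate.
- Keep the subject-level mean, SD, SE, median, minimum and maximum as supplementary.
- Take the 95% CI from the negative binomial model fitted to event counts, with the log-exposure offset. A subject-clustered interval is an alternative where events are sufficient.
- State the end date of each interval for subjects without a Visit 8 or Visit 9 date.

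The cost is one or two extra rows per table from data already derived, plus a corrected response variable in the model code. The figures will be less comparable with earlier reports that used subject-level means. A pooled rate is still affected if subjects leave because of hypoglycaemia, so it stabilises the estimate without removing that problem.

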### 3.3. Benefit/Risk Assessment

There are different ways of insulin initiation in India – twice-daily neutral protamine Hagedorn insulin or once-daily LANTUS or premixed insulin. It is increasingly becoming easier to initiate subjects on long acting insulins due to its once-in-a-day dose. Evidence from several large randomized controlled trials showed that self-titration of insulin can help to reduce levels of glycated hemoglobin (HbA1c) and fasting blood glucose (FBG) without increasing the risk of hypoglycemia. This study involving glucometer-based blood glucose measurement can further substantiate the fact that subjects can self- titrate basal insulin in India without increased risk of hypoglycemia.

More detailed information about the known and expected benefits and risks of Basaglar may be found in the Patient Information Leaflet, Package Insert, or Summary of Product Characteristics.

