### 10.3. Statistical Analyses

#### 10.3.1. General Statistical Considerations

All data will be entered, verified, and archived by a contract research organization (CRO) external to Lilly and/or at Lilly. Data listings, summaries, and analyses will be performed by a CRO under the guidance and approval of statisticians at Lilly. Statistical analysis of this study will be the responsibility of Lilly.

Any change to the data-analysis methods described in the protocol will require an amendment ONLY if it changes a principal feature of the protocol. Any other change to the data analysis methods described in the protocol, and the justification for making the change, will be described in the statistical analysis plan and/or in the clinical study report. Additional exploratory analyses will be conducted as deemed appropriate.

Safety and efficacy analyses will be conducted on the full analysis set (FAS) or safety set. These sets include all data from all enrolled subjects who take at least 1 dose of study treatment.

All tests of treatment effects will be conducted at a 2-sided alpha level of 0.05, unless otherwise stated.

The planned statistical method for the primary analysis is the calculation of the estimate and the 95% confidence interval for the incidence of total (symptomatic or asymptomatic with FBG level  $\leq 54$  mg/dL [3.0 mmol/L]) hypoglycemic events at Week 24.

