7.4 Statistical tests

This is the single arm study so no comparison tests will be performed.

The incidence of hypoglycemia will be analysed using the exact binomial method (Clopper-Pearson method) for single proportions. The change from baseline (e.g. for HbA1c, FBG levels etc) will be analysed using the general linear model and the baseline visits of the respective parameter will be considered as covariate. The rates

of hypoglycemia will be analysed using the Negative Binomial Model without categorical variable i.e. the generalized linear model and the baseline visit of HbA1c will be considered as covariate.

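### SAP 20.2.2 draws a conclusion about change in hypoglycaemia rates from a baseline-HbA1c slope test that can assess neither a change in the rate nor its level

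*SAP*

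**What the plan says.** SAP 20.2.2 models the rate of total hypoglycaemic events with a negative binomial regression that has one covariate (baseline HbA1c), an offset for log treatment exposure and no group term. Its null hypothesis, β = 0, is put in words as "The Rate of per 30 days and per subject year of total hypoglycaemic events not significantly differs depending on the Baseline HbA1c". The rule then reads: "The above hypothesis will be tested based on α (alpha)=0.05". When the p-value is not below that level, the stated conclusion is "then we will conclude that there is no statistically significant change in rates per 30 days and per subject year of total hypoglycaemic events", with the null declared accepted. An estimate, a 95% CI and a p-value are to appear in the table.

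The sample PROC GENMOD code names a response rate as the dependent variable, adds the exposure offset, and requests one ESTIMATE line, "int 1 Baseline HbA1c observed mean / exp". Only the ESTIMATE output is saved.

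SAP 20.2.3 sends nocturnal, severe, documented symptomatic and asymptomatic events to "section 20.2.2 for rates of hypoglycemic events".

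Two other places bear on this. SAP 7.4 states: "This is the single arm study so no comparison tests will be performed". Protocol 10.3.2.1 specifies the same negative binomial model with the same covariate and offset, but no hypothesis and no decision rule.

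**The concern.** The hypothesis concerns a gradient: do subjects with higher baseline HbA1c have more or fewer events? The conclusion concerns something else, a change in the hypoglycaemia rate. No such change is defined. Events are collected from Visit 2 onward in insulin-naïve subjects in one arm, and no pre-treatment or external rate enters the model. The slope does not measure the level of the rate either, and non-significance is read as acceptance of the null with no margin.

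Hypoglycaemia risk is the primary objective, and the primary analysis is estimation with a confidence interval. The rule in 20.2.2, with its extension in 20.2.3, is therefore the only written accept/reject rule on hypoglycaemia in either document. A report that followed it would carry a prespecified statement of no change in rates that the data could not have contradicted in any meaningful way.

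**Working it through.** **Inputs from the documents.** α = 0.05 with a two-sided alternative (SAP 20.2.2). n = 250 enrolled and 200 completers (protocol 10.1). 20% drop-out. 24 weeks = 168 days of treatment. The sample size reproduces: 200/0.80 = 250, and 250/0.85 = 294.1, rounded up to 295 screened. Neither document gives a power, margin or reference rate for the rate model, so there is no planned figure to reproduce there.

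**Assumptions not in the documents.** Baseline HbA1c about N(8.8, 1.0) limited to 7–11; dispersion 1 or 5; drop-out uniform over days 7–168; true rates of 0.5 to 50 per subject-year; rate ratios per 1% HbA1c of 0.7 to 1.43. Each count-model cell used 3,000 simulated trials (Monte Carlo standard error √(0.95 × 0.05/3000) = 0.004 near 0.95).

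**Step 1: the slope rule with event counts as response.** If β = 0, P(p ≥ 0.05) = 1 − 0.05 = 0.95 whatever the rate. Simulation gave 0.94–0.95 at every rate from 0.5 to 50 per subject-year, for n = 200 and 250. If β ≠ 0, the probability of the no-change statement at n = 250 was:

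| Rate ratio per 1% HbA1c | Dispersion | 0.5/yr | 2/yr | 10/yr | 50/yr |
|---|---|---|---|---|---|
| 0.9 | 5 | 0.92 | 0.89 | 0.88 | 0.89 |
| 0.8 | 5 | 0.81 | 0.74 | 0.68 | 0.66 |
| 0.7 | 5 | 0.61 | 0.43 | 0.37 | 0.34 |
| 0.8 | 1 | 0.72 | 0.40 | 0.16 | 0.10 |

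The rate enters only through power: more events make a given gradient easier to detect. In no row does the result measure how high the rate is.

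**Step 2: the p-value the program saves.** With a log link, the ESTIMATE line tests log(estimate) = 0, that is exp(estimate) = 1 in the chosen time unit. With counts, that is 1 event per year in one table and 1 per 30 days (365.25/30 = 12.2 per year) in the other. Neither is the stated null. In simulation with counts, the yearly version gave p ≥ 0.05 in about 94–95% of trials at a true rate of 1 per year and in none at 10 per year. The 30-day version gave 95% at 12.2 per year and none at 2 or 50 per year.

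**Step 3: the program as written, with a rate as response plus the offset.** Exposure is divided out twice. For a 168-day completer the offset is log(168/365.25) = log 0.46 on the yearly scale and log(168/30) = log 5.6 on the 30-day scale.

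- The saved null becomes a rate of about 0.46 per year, or 5.6 per 30 days.
- The printed rate is off by about the same factor. With 20% drop-out, mean exposure is 0.8 × 168 + 0.2 × 87.5 = 151.9 days = 0.416 years. A simple ratio approximation then gives 1.0/0.416 = 2.4 per year for a true 1.0, and 0.082/(151.9/30) = 0.082/5.06 = 0.016 per 30 days for a true 0.082. Simulation agrees: about 2.5 per year and 0.016 per 30 days.
- With β = 0 and drop-out, the slope test gave p ≥ 0.05 in 0.87–0.91 of trials (yearly) and 0.82–1.00 (30-day), so even the nominal 0.95 is not assured.

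**The case against.** The strongest reply is that the sentence is loosely worded template text. Near-identical hypothesis and acceptance wording appears for laboratory values, vital signs, HbA1c, FBG, SMBG, weight and ITSQ. Read with the stated null, it could mean only that the rate does not depend on HbA1c. On that reading, 95% acceptance of a true null is correct test size and not a missed safety signal. This is fair about intent. But the qualifier is absent from the conclusion the SAP tells the analyst to write. For the other endpoints a change from an earlier value at least exists; here it does not.

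Three stronger readings are tempting and are not supported.

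- A reader might infer that the statement is reached about 95% of the time however high the rate is. That needs counts as the response and no HbA1c effect. With a gradient the probability fell well below 0.95, and the literal program does not guarantee 0.95 even without one.
- A reader might link the rule to protocol 3.3, which speaks of self-titration "in India without increased risk of hypoglycemia". That sentence is background rationale. No passage makes 20.2.2 the evidence for it, so it needs no edit on this account.
- A reader might think the primary result is compromised. It is not: SAP 19.2.1 reports incidence with an exact 95% CI and no hypothesis test.

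It also stands that the code is labelled a sample, that the documents do not settle which p-value the table will carry, and that 20.2.2 already plans rate summaries and a confidence interval.

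**Conclusion.** The concern holds in a limited form. Followed as written, 20.2.2 and 20.2.3 yield a conclusion about change in hypoglycaemia rates that the slope test cannot support, and that sits badly with the SAP's own statement that no comparison tests will be done. This rests on the text and needs no simulation.

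The size is conditional. With a count response, the no-change statement appears in about 95% of trials if baseline HbA1c has no effect. With an effect, the probability ran from 0.92 down to 0.10 in the cases tabulated, depending on assumed gradient, dispersion and event count. The saved ESTIMATE p-value does not repair this, because its null is set by the time unit.

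The double exposure adjustment matters separately, since it distorts the reported rates themselves: roughly 2.5-fold too high on the yearly scale and about five-fold too low on the 30-day scale (0.082/0.016 = 5.1), under the assumed drop-out pattern. All of this concerns a secondary analysis and should be corrected before the rate tables are produced.

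**What to change.** In SAP 20.2.2, and so in 20.2.3:

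- Delete the null and alternative hypotheses, the acceptance rule and the p-value for the rate tables.
- State that the response is the number of events per subject, with log exposure as the offset, and change the sample program to match. Removing the p-value alone would leave wrong rates in the tables.
- Report the rate per 30 days and per subject-year with its 95% CI.
- If the HbA1c slope is kept, report it as a rate ratio per 1% baseline HbA1c with a 95% CI, labelled as an association.

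This brings the SAP into line with protocol 10.3.2.1, which gives the model without a hypothesis. The cost is a wording change, one program line and one table column. No new data are needed. The small downside is that the rate tables no longer carry a p-value.
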